5.4 TREATMENT MISALLOCATIONS

For subjects with errors in treatment allocation, they will be reported for efficacy and safety analyses as follows:

If a subject was:

- Randomized but not treated (treatment is defined as attending post baseline study visits), then they are by definition excluded from the efficacy and safety analyses as actual treatment is missing.
- Treated but not randomized, then by definition they will be excluded from the efficacy analyses since randomized treatment is missing, but will be reported under the treatment they actually received for all safety analyses.
- Randomized but took incorrect treatment, then they will be reported under their randomized treatment group for all efficacy analyses, but will be reported under the treatment they actually received for all safety analyses.

5.5 PROTOCOL DEVIATIONS

All protocol deviations will be determined and documented prior to final analysis.

The following describes any protocol deviations that relate to the statistical analyses or populations:

	Title: Statistical Analysis Plan
	Project #: IG1002 AMBAR
	Version: Final 1.0 Effective Date: 31July2018
	Protocol Version: Version 5.0 Effective Date: Feb2018

5.5.1 Deviations assessed prior to randomization

Deviations prior to the randomization are mainly deviations from the inclusion/exclusion criteria. Deviations from the inclusion/exclusion criteria will be summarized by a frequency table.

5.5.2 Deviations assessed post-randomization

Deviations post-randomization are mainly the following:

- Missing or inappropriate timing of the efficacy or safety assessments
- Deviation from the treatment scheme, e.g. incorrect timing, incorrect dose, or incorrect treatment.
- Application of prohibited concomitant medication.

Deviations from the protocol will be listed and categorized as minor or major protocol deviations prior to database lock.

6 STUDY POPULATION SUMMARY

The set of FAS patients set will be used for all study population summaries unless otherwise noted. Summaries will be presented by treatment group and overall unless otherwise noted. The 3 combined active treatment groups will also be presented for the patient disposition, demographics and the medical history.

6.1 PATIENT DISPOSITION

Patients in the FAS analysis set who completed the study and patients who withdraw from the study will be summarized using descriptive statistics. Patients who withdrew from the study will also be summarized using descriptive statistics by reason for withdrawal. The denominator for calculating the percentages will be the set of FAS patients.

Patients enrolled (defined as patients who signed the Informed Consent Form) but not randomized and reason for not being randomized will also be summarized by a frequency table. Also patients randomized but not treated and reason for not being treated will be summarized by a frequency table.

6.2 DEMOGRAPHICS

	Title: Statistical Analysis Plan
	Project #: IG1002 AMBAR
	Version: Final 1.0 Effective Date: 31July2018
	Protocol Version: Version 5.0 Effective Date: Feb2018

Demographics characteristics including age, sex, height, weight and calculated body mass index (BMI), will be tabulated and will also include age presented categorically. Missing categories will be presented if necessary.

6.3 MEDICAL HISTORY

Medical history including relevant medical/surgical history, medical history of Alzheimer’s disease, and Mini-Mental Status Examination (MMSE) will be summarized using descriptive statistics.

6.4 PRIOR MEDICATIONS

All prior medications will be coded using the World Health Organization dictionary of medical codes (WHO Drug). The incidence of prior medications will be summarized using descriptive statistics by therapeutic class and preferred term. Patients are counted only once in each therapeutic class category, and only once in each preferred term category. Prior medications will include all medications taken prior to the first day of study drug treatment. Medication which will be initiated prior to the first day of study treatment and continued after the first day of study drug will counted as both, prior and concomitant medication.

6.5 ELECTROCARDIOGRAM

Electrocardiogram findings (normal, abnormal, and missing) at baseline will be summarized using descriptive statistics.

[figure not shown]
6.6 PHYSICAL EXAMINATION

Patients with a physical examination, patients with at least 1 abnormal finding, and abnormal findings for each category will be summarized at baseline using descriptive statistics.

7 END POINTS AND COVARIATES

Baseline is defined as the last assessment prior to study drug administration (first full plasma exchange or sham treatment in the control group).

Most summaries will include the 4 treatment groups and cover the entire study period (including both the intensive and maintenance phases), but some analyses (particularly safety) may summarize a specific phase. Summary statistics will be provided for the

	Title: Statistical Analysis Plan
	Project #: IG1002 AMBAR
	Version: Final 1.0 Effective Date: 31July2018
	Protocol Version: Version 5.0 Effective Date: Feb2018

actual value and for the change from baseline for each point in time a variable is measured. Only available data will be included in these summary statistics, if not otherwise stated, no substitution of missing values will be done. In addition to the analysis at each point in time a variable is measured, for the safety variables and the biomarkers an analysis will also be performed for the last non-missing post-baseline value (end point).

Study days will be numbered relative to the first day of study drug administration. The start of treatment (Day 1) is defined as the date on which a patient receive the first study treatment. Days will be numbered relative to study start (i.e., ..., -2, -1, 1, 2, ...; with day 1 being the first administration of study treatment and day -1 being the day before the first administration of study treatment).

Protocol-defined efficacy assessments will be “slotted” to study visits based on collection date and applying the rules summarized in the following table. The study day range is the time period where assessments can be selected to populate a study visit, e.g. the assessments from study day 92 to study day 228 can be considered as assessments for the LVPE Visit 4 (month 6) visits.

Visit	Target Study Day	Study day range
Screening/Baseline		$-\infty$ to 1
FPE Visit 1 (Week 1)*	1	1
Intermediate visit (Week 7-8)	45	2 to 93
LVPE Visit 4 (Month 6)	141	94 to 184
LVPE Visit 7 (Month 9)	225	185 to 268
LVPE Visit 10 (Month 12)	309	269 to 343
Final Visit	375	344 to ∞
* Reference date for all other visits		

The slotting scheme for the CSF biomarkers will be as follows:

Visit	Target Study Day	Study day range
Screening/Baseline		$-\infty$ to 1
FPE Visit 1 (Week 1)*	1	1
Intermediate visit (Week 7-8)	45	2 to 187
Final Visit	375	188 to ∞
* Reference date for all other visits		

	Title: Statistical Analysis Plan
	Project #: IG1002 AMBAR
	Version: Final 1.0 Effective Date: 31July2018
	Protocol Version: Version 5.0 Effective Date: Feb2018

If 2 or more assessments are falling into the range of a study visit, the assessment closest to the targeted study day will be used, if 2 assessments has the same distance to the targeted study day, the assessment after the targeted study day will be used for the summary statistics. The first Full Plasma Exchange Visit (Week1) will be used as reference for the slotting of all efficacy study visits, regardless of whether or not there is any deviation from the protocol regarding to the study treatment.

The biomarkers in plasma are assessed at each plasma exchange visit prior to the exchange (pre-exchange value) and after the plasma exchange (post-exchange value). The biomarkers in plasma will be slotted as follows:

- Baseline value is the last available value prior to treatment initiation (FPE1). If there is no available value prior to the treatment initiation, the pre-treatment value of FPE1 will be used as baseline value.
- No slotting will be applied to the pre- and post-exchange values of FPE1-FPE6, the intermediate visit, and LVPE1-LVPE12.
- If LVPE12 has been performed, the final visit will be analyzed as final visit. Otherwise, the values from the final visit will be slotted to the visit subsequent to the last performed plasma exchange and analyzed as pre-exchange value, e.g. if LVPE4 is the last performed plasma exchange, the value from the final visit will be analyzed as LVPE5 pre-exchange value.

No windowing schemas will be applied to the safety data (e.g. vital signs, laboratory values, etc.). For by-visit summaries, if there are multiple assessments at a post baseline visit then the last non-missing assessment at that visit will be used for the summary. This includes assessments at the scheduled and unscheduled visits.

Summaries of clinically significant abnormal values will include all post baseline values (including scheduled, unscheduled, and early termination visits).

Descriptive statistics for continuous variables include n, mean, standard deviation, standard error of the mean, median, minimum, and maximum. Descriptive statistics for categorical variables include patient counts and percentages.

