6.1.2 Secondary Efficacy Variables

- a) Change from baseline in the cognitive, functional and neuropsychiatric scores and overall development as measured by MMSE, NPS battery, NPI, CDR-Sb, ADCS-CGIC, CSDD and C-SSRS. (6 measurements: week -3, -2 or -1 and 7-8; months 6, 9, 12 and 14) and QoL-AD, RUD-Lite[®] (5 measurements: weeks -3, -2 or -1; months 6, 9, 12 and 14). Moreover the optional questionnaires like OAS and ABS could be used at any visit in case any sign of aggression or restlessness.
- b) Variation in levels of A β ₁₋₄₀ and A β ₁₋₄₂ in CSF in the period between baseline lumbar puncture (before the start of the Intensive treatment period) and lumbar puncture immediately after the end of the last low-volume plasmapheresis (whenever this may be)
- c) Variation in the levels of A β ₁₋₄₀ and A β ₁₋₄₂ in CSF between the finalization and beginning of each of the 2 treatment periods.
- d) Levels of A β ₁₋₄₀, A β ₁₋₄₂, T-tau and P-tau in CSF throughout the study.

- e) Plasma levels of A β ₁₋₄₀ and A β ₁₋₄₂ before and after each plasma exchange for both treatment periods.
- f) Structural changes in volume of the hippocampus, posterior cingulate area, and other associated areas by MRI. Five measurements will be made (weeks -3, -2 or -1 and 7-8; months 6, 9 and 14).
- g) Variation in FDG-PET patterns (4 measurements: weeks -3, -2 or -1 and 7-8; months 9 and 14).

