6.2.3 Weeks 7 to 8 – Intermediate visit (Window range +/- 2 days)

Plasma samples will be collected from the subjects (control and full plasma exchange group) to allow the pertinent tests. Additional plasma samples will be collected each time for storage at -70°C and possible future assays.

The following tests will be made: biomarkers of AD (A β -40, A β -42, β -secretase, γ -secretase, cholesterol, LDL, HDL, VLDL, and C-reactive protein, rheumatoid factor, IL-1b, IL-6, ferritin, TNF- α) and plasma IgG.

During the visit medical history will be checked with the recording of any anomalies. Concomitant medication is also to be registered, together with any adverse event detected since the last visit or since the last plasma exchange session.

Central catheter will be also extracted during this intermediate visit.

After the intensive plasma exchange period (weeks 1 to 6) and before Maintenance period, lumbar puncture will be performed to assess the levels of A β -40, A β -42, P-tau, T-tau and other Alzheimer's disease biomarkers together with standard tests (cell counts, glucose, proteins and albumin). Time collection for the CSF must be between 8am and 12am.

During this intermediate visit (weeks 7 to 8) the following cognitive impairment and behavioral tests will be made: ADAS-Cog, MMSE, NPS battery, ADCS-ADL, NPI, CDR-Sb, ADCS-CGIC, CSDD and CSSRS. Likewise, anxiety and restlessness tests will be made based on the Overt Aggression Scale (OAS) and the Agitated Behavior Scale (ABS), if considered opportune.

During the study period between week 7 and 8, a FDG-PET and an MRI will be also carried out.

Control group

The control group will undergo simulated (sham) central catheter removal and will follow the same schedule of assessments as the treated groups

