There will be 3 treatment groups. A maximum of 12 plasmaphereses will be performed, one plasmapheresis per month. In the first treatment group there will be 9 plasmaphereses with infusion of albumin 20% (200 mL, 40 g) at months 4, 5, 6, 8, 9, 10, 12, 13 and 14 and 3 plasmaphereses with infusion of IVIG (20 g) at months 3, 7 and 11. In the second treatment group, the schedule will be the same as previous but with half of the dose of albumin 20% (100 ml, 20 g) and IVIG (10 g). The third treatment group will follow the same schedule but only half-dose albumin (100 ml, 20 g) will be administered in each of the 12 plasmaphereses, that is, this group will not receive IVIG. The plasma removed and the albumin infused after the procedure depends on patient's weight (see Table 1, Appendix 10).

The subject will remain in the center throughout the procedure and then for as long as needed to ensure a safe return home, under conditions similar to before the procedure.

Before each plasmapheresis, a physical examination will be made, with the recording of any anomalies. Concomitant medication is also to be registered, together with any adverse event detected since the last visit or since the last plasma exchange session.

The anxiety and restlessness tests, if necessary, will be performed before each plasmapheresis, and between 15-30 minutes after the administration of albumin or IVIG. These tests will be carried out by the same patient supervisor.

Vital signs (axillary temperature, heart and respiratory rate, and blood pressure) will be determined 15-30 minutes before plasmapheresis, during and again 15-30 minutes after the administration of albumin or IVIG and as often as considered opportune by the investigator.

Any adverse event during or after the procedure, will be recorded.

A FDG-PET will be carried out at months 9 and an MRI also will be carried out at months 6, and 9.

Control group

The control group will undergo simulated (sham) low-volume plasma exchanges but will follow the same schedule of assessments.

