6.2.5 Final Visit (Month 14)

During the final visit medical history will be checked with the recording of any anomalies. Concomitant medication is also to be registered, together with any adverse event detected since the last visit or since the last plasma exchange session.

Plasma samples will be collected from the subjects (control and treatment group) to allow the pertinent tests. Additional plasma samples will be collected each time for storage at -70°C and possible future assays.

The following parameters will also be evaluated: biomarkers of AD (A β -40, A β -42, β -secretase, γ -secretase, cholesterol, LDL, HDL, VLDL, C-reactive protein, rheumatoid factor, IL-1b, IL-6, ferritin, TNF- α), coagulation factors (prothrombin time (Quick), aPTT, calcium and fibrinogen), proteinogram (total proteins, albumin, α_1 -globulina, α_2 -globulina, β -globulina, γ -globulina and IgG), other liver or kidney biochemical markers (AST, ALT, bilirubin, LDH and creatinine), troponin and serology (anti-HIV and HCV antibodies, and HBsAg antigen). In addition, a blood cell count will be performed, including: hematocrit, hemoglobin and erythrocytes, platelets and leukocytes (if an abnormal leukocyte count is recorded, it will be obligate to specify neutrophils, basophils, eosinophils, lymphocytes and monocytes).

During the final visit a MRI and a FDG-PET will also be performed.

The following tests will be performed to measure cognition, functionality, behavior, global evolution, impression and depression: ADAS-Cog, MMSE, NPS battery, ADCS-ADL, NPI, CDR-Sb, ADCS-CGIC, CSDD, CSSRS, QoL-AD and RUD-Lite[®] which are to be administered as indicated in the corresponding section. Likewise, anxiety and restlessness tests will be made based on the Overt Aggression Scale (OAS) and the Agitated Behavior Scale (ABS), whenever considered opportune.

Furthermore, it is obligatory to perform lumbar puncture, to collect CSF samples and assess the levels of A β -40, A β -42, P-tau, T-tau, β -secretase, γ -secretase, cholesterol, LDL, HDL, VLDL, C-reactive protein, IL-1b, IL-6, ferritin, TNF- α) and to perform standard CSF tests (cell counts, glucose, proteins and albumin).

These evaluations are considered to be the final data.

Control group

The control group will undergo the same schedule of assessments.

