| ECG | X | | | | | | | | | | | | | | | | | | | | | | | |
| Genetic Markers | X | | | | | | | | | | | | | | | | | | | | | | | |
| Vital signs | X | | | B+D+ A | B+D+ A | B+D+ A | B+D+ A | B+D+ A | B+D+ A | | B+D+ A | B+D+ A | B+D+ A | B+D+ A | B+D+ A | B+D+ A | B+D+ A | B+D+ A | B+D+ A | B+D+ A | B+D+ A | B+D+ A | B+D+ A | |
| Adverse Events | | | | X | X | X | X | X | X | X | X | X | X | X | X | X | X | X | X | X | X | X | X | X |
| Concomitant Medication | | X | | X | X | X | X | X | X | X | X | X | X | X | X | X | X | X | X | X | X | X | X | X |
| Central catheter implantation | | X | | | | | | | | | | | | | | | | | | | | | | |
| Central catheter extraction | | | | | | | | | | X | | | | | | | | | | | | | | |
| Plasmapheresis | | | | FPE | FPE | FPE | FPE | FPE | FPE | | LVPE | LVPE | LVPE | LVPE | LVPE | LVPE | LVPE | LVPE | LVPE | LVPE | LVPE | LVPE | LVPE | |
| Albumin 5% | | | | 35-45 ml/kg | 35-45 ml/kg | 35-45 ml/kg | 35-45 ml/kg | 35-45 ml/kg | 35-45 ml/kg | | | | | | | | | | | | | | | |
| 1 st and 2 nd Arm: Albumin 20% | | | | | | | | | | | - | 200 100m L | 200 100 mL | 200 100 mL | - | 200 100 mL | 200 100 mL | 200 100 mL | - | 200 100m L | 200 100 mL | 200 100m L | | |
| 1 st and 2 nd Arm: IgIV | | | | | | | | | | | 20 g 10 g | - | - | - | 20 g 10 g | - | - | - | 20 g 10 g | - | - | - | | |
| 3 rd Arm: Albumin 20% | | | | | | | | | | | 100 mL | 100 mL | 100 mL | 100 mL | 100 mL | 100 mL | 100 mL | 100 mL | 100 mL | 100 mL | 100 mL | 100 mL | 100 mL | |

| Visit | Screening | | Randomization | FPE1 | FPE2 | FPE3 | FPE4 | FPE5 | FPE6 | IV | LVP E1 | LVP E2 | LVP E3 | LVP E4 | LVP E5 | LVP E6 | LVP E7 | LVP E8 | LVP E9 | LVP E10 | LVP E11 | LVP E12 | Final |
|---------------------------------------|-----------|----|---------------|-------|-------|-------|-------|-------|-------|-------|--------|--------|--------|--------|--------|--------|--------|--------|--------|---------|---------|---------|-------|
| Time / Weeks | -3 | -2 | -1 | 1 | 2 | 3 | 4 | 5 | 6 | 7-8 | 9 | 13 | 17 | 21 | 25 | 29 | 33 | 37 | 41 | 45 | 49 | 53 | 54-55 |
| Window Range (days) | | | | +/- 1 | +/- 1 | +/- 1 | +/- 1 | +/- 1 | +/- 1 | +/- 2 | +/- 5 | +/- 5 | +/- 5 | +/- 5 | +/- 5 | +/- 5 | +/- 5 | +/- 5 | +/- 5 | +/- 5 | +/- 5 | +/- 5 | +/- 2 |
| Months | -1 | | | 1 | | | 2 | | | | 3 | 4 | 5 | 6 | 7 | 8 | 9 | 10 | 11 | 12 | 13 | 14 | 14 |
| Study Schedule | | | | | | | | | | | | | | | | | | | | | | | |

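### The SAP's CSF windows count a drop-out's puncture from day 188 as Final, after as few as 5 of 12 low-volume sessions, and let a maintenance-phase puncture stand in for a missing end-of-intensive one

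*SAP*

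**What the plan says.** SAP section 7 explains its windows by stating that "The study day range is the time period where assessments can be selected to populate a study visit". If two or more assessments fall in one window, "the assessment closest to the targeted study day will be used". The CSF table, introduced by the line "The slotting scheme for the CSF biomarkers will be as follows", has only two post-baseline rows: Intermediate (target day 45, days 2 to 187) and Final (target day 375, day 188 with no upper limit).

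The efficacy table in the same section has five post-baseline rows. Intermediate ends at day 93, Month 9 covers days 185 to 268, Month 12 covers days 269 to 343, and Final opens at day 344. For plasma biomarkers, section 7 uses the Final label only if LVPE12 was performed. Otherwise the value goes to the visit after the last exchange received.

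The protocol fixes the timing of the intermediate sample in 6.2.3: "After the intensive plasma exchange period (weeks 1 to 6) and before Maintenance period, lumbar puncture will be performed". Section 6.2.5 says of the final visit: "Furthermore, it is obligatory to perform lumbar puncture, to collect CSF samples". Section 4.4 schedules a final visit for withdrawn patients, and the end of 6.2.5 lets an early one omit assessments case by case. Secondary variable (c) in protocol 6.1.2 is the change in CSF amyloid "in CSF between the finalization and beginning of each of the 2 treatment periods".

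SAP 7.1.11 lists CSF amyloid and tau as secondary efficacy parameters. SAP 9.1.4 and 9.2.5 analyse biomarkers at each time point by ANCOVA, and 7.3.1 also summarises the change from the intermediate to the final visit.

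**The concern.** The intermediate puncture marks the end of the intensive phase, when the three active arms have had the same treatment. The final puncture marks the end of the maintenance phase, when they have not. Variable (c) and the intermediate-to-final change both depend on that boundary and on Final meaning a comparable amount of maintenance treatment.

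Windows that meet at day 187/188 do not secure either. Final can mix patients with 5 to 12 low-volume sessions. Intermediate can contain samples taken after treatment has begun to differ by arm. SAP 9.1.1 itself warns, for the co-primaries, that drop-out may not be random. Early withdrawals labelled Final could therefore affect the arm comparisons, in a direction the documents do not let one predict.

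**Working it through.** **Week-to-day conversion.** Protocol Appendix 8 gives visits in weeks and the SAP gives target days. Take study day = 7 × (week − 1) + 1. Weeks 21, 33 and 45 (LVPE4, 7 and 10) give days 141, 225 and 309, exactly the SAP's own targets, so the conversion can be used.

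**Visit days from the same formula.**
- Weeks 7-8: days 43 to 56, or 41 to 58 with the ±2-day visit window.
- LVPE1, week 9: day 57.
- LVPE2, week 13: day 85.
- LVPE5, week 25: day 169.
- LVPE6, week 29: day 197.
- LVPE9, week 41: day 281.
- LVPE11, week 49: day 337.
- LVPE12, week 53: day 365.

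Each low-volume session has a ±5-day window.

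**Final window.** Day 188 falls between LVPE5 (169) and LVPE6 (197), so the window admits patients with 5 of 12 sessions. It opens 375 − 188 = 187 days before its own target. In the efficacy table, days 188 to 268 are Month 9 and days 269 to 343 are Month 12. One early final visit can thus be Month 9 for ADAS-Cog and Final for CSF.

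**Intermediate window.** From LVPE1 to the cut is 187 − 57 + 1 = 131 days. The low-volume sessions span 365 − 57 + 1 = 309 days, so the window takes in 131/309 = 42% of that span, LVPE1 to LVPE5. In the first arm the protocol has "3 plasmaphereses with infusion of IVIG (20 g) at months 3, 7 and 11", and the second arm follows the same schedule at half dose. Months 3 and 7 are LVPE1 and LVPE5, so two of the three IVIG sessions fall inside the window.

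**Which value is used.** If an on-time puncture exists (say day 45) together with a withdrawal puncture at day 160, the first is 0 days and the second 115 days from target. The on-time value is used, and the later one survives only in the last-value analysis. If there was no week 7-8 puncture, the day-160 sample, taken after LVPE4, becomes the Intermediate value.

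**How many enter Final early.** Planned drop-outs: 364 − 312 = 52. Assume withdrawals spread evenly over days 1 to 374 and a puncture at every early final visit. Days 188 to 343 are 156 days, and 52 × 156/374 = 21.7, about 22. Against 312 completers, all assumed punctured, that is 22/(312 + 22) = 6.6% of Final values. If half the early final visits included a puncture the count would be about 11; if none did, 0. Withdrawals concentrated inside days 188 to 343 would raise it.

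**How many maintenance samples become Intermediate.** On the same assumptions, 52 × 131/374 = 18.2 withdrawals fall in days 57 to 187. Only those without a puncture nearer day 45 would be mislabelled. The documents give no rate of missed week 7-8 punctures, so no count can be stated; for withdrawals, 18 is a ceiling under these assumptions.

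**The case against.** The best defence is protocol variable (b): the CSF change from baseline to the puncture after the last low-volume session, at whatever time that occurs. For (b), an early last sample is the intended value. Variable (c) can also be read, for a drop-out, as ending when that patient's treatment ended. SAP section 7 slots from FPE1 irrespective of treatment deviations, so keeping partly treated patients is deliberate. This stands as far as (b) goes, but the SAP already serves (b) with its last non-missing value analysis. The day-188 cut serves neither purpose: it leaves withdrawals before day 188 out of Final and mixes 5 to 12 sessions in a result labelled with target day 375.

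It is also fair that the efficacy windows are not clean. Efficacy Intermediate runs to day 93, past LVPE1 and LVPE2, and efficacy Final opens before LVPE12. The difference is one of degree, but it is large: at day 344 a patient on schedule has had 11 of 12 sessions, against 5 at day 188.

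Three stronger readings are tempting and do not hold.
- A reader might infer that every maintenance puncture is counted as Intermediate. The closest-to-target rule prevents that whenever a puncture nearer day 45 exists.
- A reader might infer that all drop-outs become Month 14. Only those punctured from day 188 do.
- A reader might call 187 a calculation error. The efficacy cuts (93, 184, 268, 343) lie within a day of the midpoints between targets (93, 183, 267, 342), whereas the CSF midpoint is (45 + 375)/2 = 210. The SAP states no midpoint rule, however, and a cut at 210 would push Intermediate further into maintenance.

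**Conclusion.** The point holds in limited form. By-visit CSF Final and the intermediate-to-final change can include drop-outs with 5 to 11 of the 12 low-volume sessions, at odds with the SAP's own handling of cognition and plasma. CSF Intermediate can include maintenance-phase samples for patients who lack the week 7-8 puncture, at odds with protocol 6.2.3.

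The size is about 22 early values in Final if 52 withdrawals are evenly timed and all are punctured. The likely number is smaller because punctures may be skipped. The Intermediate mislabelling cannot be counted from the documents.

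The affected endpoints are secondary, with no formal control across secondary endpoints (SAP 4.2), and the ADAS-Cog and ADCS-ADL analyses are untouched. Nor do the documents support saying that a planned biomarker-cognition analysis is damaged: SAP 7.3.1 offers such correlations only as optional exploration and specifies no pairing of visits. The change should be made because it is specific and cheap.

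**What to change.** Change the CSF table in SAP section 7 and add a short rule.
- **Final:** open the window at day 344, as for the efficacy Final visit.
- **Intermediate:** accept punctures after the last full exchange received and before LVPE1, and no later than day 93, the efficacy Intermediate limit.
- **Where those anchors are missing:** Version 1.0 controls had no sham sessions (SAP 2.1), and some patients never reach LVPE1. For both, use study days alone, from the start of weeks 7-8 (day 43, or 41 with the visit window) to day 93.
- **All other early-withdrawal punctures:** keep them in the existing last-value analysis, which serves variable (b), and list the study day of each.

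No new data are needed and nothing is lost from the last-value analysis. The cost is fewer CSF Final values, up to about 22 under the assumptions above, and a few fewer Intermediate values. A maintenance puncture in a patient who also has an on-time one stays outside the by-visit analysis, as it does now.

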7.1.1 Alzheimer’s Disease Assessment Scale – Cognitive (ADAS-Cog)

[figure not shown]
The ADAS-Cog Scale is a questionnaire that assesses cognitive performance in 12 different domains. The domains (and the maximum score) are: (word recall (10), commands (5), constructional praxis (5), delayed word-recall task (10), naming objects/figures (5), ideation praxis (5), orientation (8), word recognition (12), remembering test instructions (5), comprehension (5), word finding difficulties (5), and spoken language ability (5). A total score can be derived by summing across all domains (0-80). Within each domain, and for the total, a higher score indicates more cognitive impairment.

The total score will be analyzed as continuous variables, and will be summarized at each time point.

The total ADAS-Cog score at 14 months is the end point for the primary efficacy analysis. The other point in time will be regarded as secondary end points.

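### Under the SAP's visit slotting, a Month 12 assessment that is at least 35 days late can replace a final visit that is also late as the primary Month 14 value

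*SAP*

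**What the plan says.** All of the slotting text is in SAP section 7 (End Points and Covariates).

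- **Basis.** The SAP states that "efficacy assessments will be “slotted” to study visits based on collection date". The first full plasma exchange "will be used as reference for the slotting of all efficacy study visits, regardless of whether or not there is any deviation", so treatment delays do not move the targets.
- **Windows.** The Month 12 row (target day, then range) reads "LVPE Visit 10 (Month 12) 309 269 to 343". The last row reads "Final Visit 375 344 to" infinity.
- **Two assessments in one window.** In that case "the assessment closest to the targeted study day will be used". For ties, "if 2 assessments has the same distance to the targeted study day, the assessment after the targeted study day will be used".
- **Worked example.** For Month 6 the text says that "the assessments from study day 92 to study day 228 can be considered as assessments for the LVPE Visit 4 (month 6) visits", while the table beneath it gives days 94 to 184.
- **Role of the slot.** SAP 7.1.1 states: "The total ADAS-Cog score at 14 months is the end point for the primary efficacy analysis". SAP 7.1.2 says the same for ADCS-ADL. The primary MMRM in SAP 9.1.1 uses month (2, 6, 9, 12, 14) as a factor.
- **Contrast.** For plasma biomarkers the same section keeps the final visit as the final visit whenever LVPE12 was performed. The co-primary scores have no such rule.

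**The concern.** The boundary between the last two slots lies about halfway between their targets, and the last slot has no upper limit. A patient whose whole schedule runs late enough will have both LVPE10 and the final visit in the last slot. LVPE10 is then the nearer to day 375, so the rule selects it.

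The primary time point would then carry a score taken at LVPE10, before LVPE11 and LVPE12. The assessment made at the end of treatment would be left out of the primary MMRM and the Month 14 ANCOVA, although it was completed. Nothing in the SAP says that this is intended. Separately, a programmer cannot follow both the Month 6 example and the table.

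**Working it through.** **Inputs.** The targets, windows, nearest-day rule and tie rule come from SAP section 7. Visit weeks and the ±5-day maintenance window come from Protocol Appendix 8 and section 6.2.4.

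**Reproducing the plan's figures.** With day = (week − 1) × 7 + 1, LVPE10 in week 45 gives 44 × 7 + 1 = 309, as stated. Week 54 covers days 372 to 378, which contains the final target of 375. The midpoint of the two targets is (309 + 375)/2 = 342; the SAP ends the Month 12 slot at day 343, one day later.

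**Both visits slip by d days.** LVPE10 is on day 309 + d and the final visit on day 375 + d. Their distances from day 375 are |66 − d| and d. LVPE10 is nearer once 66 − d < d, that is d > 33, and it stays nearer beyond d = 66 because d − 66 < d. It enters the window only when 309 + d ≥ 344, that is d ≥ 35. The window is therefore the binding condition.

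| d | LVPE10 day (distance) | Final visit day (distance) | Used as Month 14 |
|---|---|---|---|
| 0 | 309 (outside window) | 375 (0) | Final visit |
| 34 | 343 (outside window) | 409 (34) | Final visit |
| 35 | 344 (31) | 410 (35) | LVPE10 |
| 44 | 353 (22) | 419 (44) | LVPE10 |
| 66 | 375 (0) | 441 (66) | LVPE10 |
| 80 | 389 (14) | 455 (80) | LVPE10 |

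**Unequal slips.** With LVPE10 on day m (344 to 375) and the final visit on a later day f, LVPE10 is chosen when f − 375 > 375 − m, that is f > 750 − m.

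- LVPE10 on day 344 displaces a final visit on day 407 or later.
- On day 350 the threshold is day 401; on day 360, day 391; on day 370, day 381.
- With the final visit on day 375 exactly, its distance is 0 and it is always kept.

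**Visits inside the protocol window.** If the ±5 days run from the first exchange, LVPE10 falls on days 304 to 314 and cannot reach day 344.

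**Knock-on effect if all visits slip equally.** Month 9 moves to day 225 + d. For d = 35 to 43 this is days 260 to 268, so the Month 12 slot is empty. At d = 44 it is day 269, so the Month 9 score fills the Month 12 slot, and Month 6 (141 + 44 = day 185) fills the Month 9 slot.

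**Month 6 example.** Days 92 to 228 overlap the intermediate-visit window (2 to 93) and the Month 9 window (185 to 268), including the Month 9 target of day 225.

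**The case against.** **The nearest-day rule minimises timing error.** This is true. At d = 35 it takes a score 31 days early in place of one 35 days late. Choosing between them is a choice between equal time since the first exchange and completed exposure, and either can be defended. The SAP does not say that it is making this choice, and for plasma biomarkers it chooses the other way.

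**35 days is seven times the visit window.** This limits the reach. The documents do not say whether windows run from the first exchange or from the preceding visit. If they chain (an assumption), slip by LVPE10 could reach 5 × 1 + 2 + 10 × 5 = 57 days with no formal deviation. If they do not chain, only patients outside their windows are exposed.

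**Other analyses cover it.** In part. The random slope model in SAP 9.1.1 uses every observation at its actual study day and is unaffected. SAP 5.5.2 lists inappropriate timing of assessments as a deviation, and patients with major breaches are left out of the per-protocol repeat. Neither determines study success.

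**The selection sentence mentions summary statistics.** It does, but the MMRM needs one record per patient per month. SAP 9.1.1 contrasts the random slope model's actual days with the slotted time points, so the slots evidently feed the MMRM.

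**Conclusion.** The mechanism follows from the written rule. It needs LVPE10 on day 344 or later and a final visit farther than LVPE10 from day 375. Under equal slip that means every delay of 35 days or more. The primary MMRM and the Month 14 ANCOVA are exposed for both co-primary endpoints.

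Three stronger readings are tempting and are not supported:

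- **That any delayed Month 12 visit replaces the final visit.** A slip below 35 days has no effect, nor does a late LVPE10 followed by an on-time final visit.
- **That affected values are taken about two months early.** The 66 days are the gap to the patient's own late final visit. Relative to day 375, a substituted LVPE10 score is at most 31 days early (day 344), exactly on target at d = 66, and late beyond that.
- **That the result is tilted towards the active arms.** Protocol 5.2.1 ties coagulation suspensions to the intensive period and does not expect relevant alterations in maintenance. Sham patients also receive a real peripheral line (Appendix 9). Catheter removal under the fever guideline, and any thromboembolic complication, lead to withdrawal (Appendices 11 and 12), so they produce dropouts and not late final visits.

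Any rate of replacement or bias in points would rest on assumed delays and an assumed rate of decline. The point is a correctable ambiguity at the primary time point, with no demonstrated bias. The Month 6 contradiction is editorial and does not touch Month 14.

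**What to change.** Add to SAP section 7, for efficacy scores:

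1. The nominal Final Visit is slotted to Month 14 when LVPE12 was performed, and the nominal LVPE10 assessment to Month 12. Other scheduled assessments likewise keep their nominal visit.
2. Day windows and the nearest-day rule apply only to unscheduled and early-termination assessments.
3. The Month 6 example reads days 94 to 184, to match the table.

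The cost is a few sentences, to be settled before database lock and unblinding. Patients on schedule are unaffected. The small downside is that some Month 14 values will come from well after day 375 (35 days or more under equal slip). The random slope analysis on actual study day, already planned, can check whether that matters.
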